**Table 3. Classification of Adverse Events by Intensity**

**MILD:** An event that is easily tolerated by the patient, causing minimal discomfort and not interfering with everyday activities.

**MODERATE:** An event that is sufficiently discomforting to interfere with normal everyday activities.

**SEVERE:** An event that prevents normal everyday activities.

**Table 4. Classification of Adverse Events by Relationship to Study Drug**

UNRELATED: This category applies to those AEs that are clearly and incontrovertibly because of extraneous causes (disease, environment, etc).
UNLIKELY: This category applies to those AEs that are judged to be unrelated to the test drug but for which no extraneous cause may be found. An AE may be considered unlikely to be related to study drug if or when it meets 2 of the following criteria: (1) it does not follow a reasonable temporal sequence from administration of the test drug (2) it could readily have been produced by the patient's clinical state, environmental or toxic factors, or other modes of therapy administered to the patient (3) it does not follow a known pattern of response to the test drug or (4) it does not reappear or worsen when the drug is readministered.
POSSIBLY: This category applies to those AEs for which a connection with the test drug administration appears unlikely but cannot be ruled out with certainty. An AE may be considered possibly related if or when it meets 2 of the following criteria: (1) it follows a reasonable temporal sequence from administration of the drug; (2) it could not readily have been produced by the patient's clinical state, environmental or toxic factors, or other modes of therapy administered to the patient or (3) it follows a known pattern of response to the test drug.
PROBABLY: This category applies to those AEs that the Investigator feels with a high degree of certainty are related to the test drug. An AE may be considered probably related if or when it meets 3 of the following criteria: (1) it follows a reasonable temporal sequence from administration of the drug (2) it could not be reasonably explained by the known characteristics of the patient's clinical state, environmental or toxic factors, or other modes of therapy administered to the patient (3) it disappears or decreases on cessation or reduction in dose (note that there are exceptions when an AE does not disappear upon discontinuation of the drug yet drug-relatedness clearly exists; for example, as in bone marrow depression, fixed drug eruptions, or tardive dyskinesia); or (4) it follows a known pattern of response to the test drug.
DEFINITELY: This category applies to those AEs that the Investigator feels are incontrovertibly related to test drug. An AE may be assigned an attribution of definitely related if or when it meets all of the following criteria: (1) it follows a reasonable temporal sequence from administration of the drug(2) it could not be reasonably explained by the known characteristics of the patient's clinical state, environmental or toxic factors, or other modes of therapy administered to the patient (3) it disappears or decreases on cessation or reduction in dose and recurs with reexposure to drug (if rechallenge occurs); and (4) it follows a known pattern of response to the test drug.

Abbreviation: AE, adverse event.

### **12.7.2 Adverse Events of Special Interest**

An AESI (serious or nonserious) is one of scientific and medical concern specific to the Sponsor's product or program, for which ongoing monitoring and rapid communication by the Investigator to the Sponsor could be appropriate. Such an event might require further investigation in order to characterize and understand it.

For the purposes of this study, the following AEs are classed as AESIs:

- Vivid and/or unpleasant dreams
- Difficulty initiating or maintaining sleep

Such AESI should be recorded in the eCRF and reported to the medical monitor via email.

### **12.7.3 Serious Adverse Events**

An SAE is any untoward medical occurrence, in the view of either the Investigator or Sponsor, that:

- Results in death
- Is life-threatening

- Results in inpatient hospitalization or prolongation of existing hospitalization
- Results in persistent or significant disability/incapacity
- Is a congenital anomaly/birth defect

Other important medical events that may not be immediately life-threatening or result in death or hospitalization, based upon appropriate medical judgment, are considered SAEs if they are thought to jeopardize the patient and/or require medical or surgical intervention to prevent one of the outcomes defining an SAE. Serious AEs are critically important for the identification of significant safety problems; therefore, it is important to take into account both the Investigator's and the Sponsor's assessment. If either the Sponsor or the Investigator believes that an event is serious, the event must be considered serious and evaluated by the Sponsor for expedited reporting.

#### **12.7.4 Serious Adverse Event Reporting**

An SAE occurring from the time informed consent is obtained, during the study, or within 14 days of stopping the treatment must be reported to the [REDACTED] Safety and Pharmacovigilance group and will be communicated to the Sponsor. Any such SAE because of any cause, whether or not related to the study drug, must be reported within 24 hours of occurrence or when the Investigator becomes aware of the event. Notification can be made using the dedicated fax line or email for the [REDACTED] pharmacovigilance group:

[REDACTED]  
[REDACTED]  
[REDACTED]

If the Investigator contacts the [REDACTED] pharmacovigilance group by telephone, then a written report must follow within 24 hours and is to include a full description of the event and sequelae in the format detailed in the SAE reporting form.

The event must also be recorded on the standard AE eCRF. Preliminary reports of SAEs must be followed up by detailed descriptions later on, including clear and anonymized photocopies of hospital case reports, consultant reports, autopsy reports, and other documents when requested and applicable. Serious AE reports must be made whether or not the Investigator considers the event to be related to the investigational drug.

Appropriate remedial measures should be taken to treat the SAE, and the response should be recorded. Clinical, laboratory, and diagnostic measures should be employed as needed in order to determine the etiology of the problem. The Investigator must report all additional follow-up evaluations to the [REDACTED] Safety and Pharmacovigilance group within 24 hours of becoming aware of the additional information or as soon as is practicable. All SAEs will be followed up until the Investigator and Sponsor agree the event is satisfactorily resolved.

Any SAE that is not resolved by the end of the study or upon discontinuation of the patient's participation in the study is to be followed up until it either resolves, stabilizes, returns to baseline values (if a baseline value is available), or is shown to not be attributable to the study drug or procedures.

### **12.7.5 Suspected Unexpected Serious Adverse Reactions**

Any AEs that meet all of the following criteria will be classified as suspected unexpected serious adverse reactions (SUSARs) and reported to the appropriate regulatory authorities in accordance with applicable regulatory requirements for expedited reporting:

- Serious
- Unexpected (i.e., the event is not consistent with the safety information in the Investigators Brochure)
- There is at least a reasonable possibility that there is a causal relationship between the event and the study treatment

The Investigator will assess whether an event is causally related to study treatment. The Sponsor ( [REDACTED] ) will consider the Investigator's assessment and determine whether the event meets the criteria for being reportable as a 7-day or 15-day safety report. SUSARs that are fatal or life-threatening SUSARs must be reported to the regulatory authorities and the institutional review boards (IRBs; where required) within 7 days after the Sponsor ( [REDACTED] ) has first knowledge of them, with a follow-up report submitted within a further 8 calendar days. Other SUSARs must be reported to the relevant regulatory authorities and the IRBs within 15 calendar days after the Sponsor ( [REDACTED] ) first has knowledge of them.

The Sponsor ( [REDACTED] ) is responsible for reporting SUSARs and any other events required to be reported in an expedited manner to the regulatory authorities and for informing Investigators of reportable events, in compliance with applicable regulatory requirements within specific timeframes. Investigators will notify the relevant IRBs of reportable events within the applicable timeframes.

### **12.7.6 Pregnancy**

Women of childbearing potential (WOCBP) must have a negative pregnancy test at Screening, Baseline, and follow-up. After administration of study drug, any known cases of pregnancy in female patients or female partners of male patients will be reported until the patient completes or withdraws from the study. The pregnancy will be reported immediately by faxing/emailing a completed pregnancy report to the Sponsor (or designee) within 24 hours of knowledge of the event. The pregnancy will not be processed as an SAE; however, the Investigator will follow-up with the patient/patient partner until completion of the pregnancy and must assess the outcome in the shortest possible time but not more than 30 days after completion of the pregnancy. The Investigator should notify the Sponsor (or designee) of the pregnancy outcome by submitting a follow-up pregnancy report. If the outcome of the pregnancy involved spontaneous or

therapeutic abortion (any congenital anomaly detected in an aborted fetus is to be documented), stillbirth, neonatal death, or congenital anomaly, the Investigator will report the event by faxing/emailing a completed pregnancy report form to the Sponsor (or designee) within 24 hours of knowledge of the event.

Upon discontinuation from the study, only those procedures that would not expose the patient to undue risk will be performed. The Investigator should also be notified of pregnancy occurring during the study but confirmed after completion of the study. In the event that a patient/patient partner is subsequently found to be pregnant after inclusion of the patient in the study, any pregnancy will be followed to term, and the status of mother and child will be reported to the Sponsor after delivery.

#### **12.7.7 Overdose**

The Investigator must immediately (within 24 hours) notify the Sponsor medical monitor, by email, of any occurrence of overdose with study drug. An overdose is classed as the patient taking more than 1 tablet in a calendar day.

## **13 PHARMACOKINETICS**

### **13.1 Pharmacokinetic Sampling**

#### **13.1.1 Blood Samples**

Blood samples for PK analysis of SUVN-G3031 levels will be collected at the time points indicated in the Schedule of Assessments ([Table 1](#)). The actual date and time of each blood sample collection will be recorded.

Details of PK blood sample collection, processing, storage, and shipping procedures are provided in a separate Laboratory Manual.

#### **13.2 Pharmacokinetic Analytical Methodology**

The concentration of study drug will be determined from the plasma samples using a validated analytical method. Details of the method validation and sample analysis will be included with the final clinical study report.

## 14 STATISTICAL ANALYSIS

A SAP will be prepared after the protocol is approved. This document will provide further details regarding the definition of analysis variables and analysis methodology to address all study objectives. The SAP will serve as a complement to the protocol and supersedes it in case of differences.

The statistical evaluation will be performed using SAS® software version 9.4 or higher (SAS Institute, Cary, NC). All data will be listed, and summary tables will be provided.

Summary statistics will be presented by treatment group. For continuous variables, data will be summarized with the number of patients (n), mean, SD, standard error of mean, median, minimum, and maximum by treatment group. For categorical variables, data will be tabulated with the number and proportion of patients for each category by treatment group.

An unblinded interim analysis is planned when approximately 50% of patients have completed 14 days of treatment (Visit 3 completed). This interim analysis is for the purpose of sample size re-estimation, and futility will not be examined. Interim analysis will occur under the supervision of an independently charted DMC. See [Section 7.1.4](#).

### 14.1 Determination of Sample Size

This study plans to randomize 114 patients, using 1:1:1 treatment allocation (stratified by at least 30% each by reported cataplexy patient history, Na-1 or Na-2 respectively), 38 to each treatment group. Using an SD of 5.0, N = 38 randomized patients per group will provide 80% power, to detect a treatment difference over placebo of 3.5 points or greater on the MWT at a 2-sided Type I error level of 0.05, assuming a dropout rate of 10%.

Because of the unknown prognostic importance of a history of cataplexy with EDS on study outcome, a stratification factor will be included based upon that clinical presentation.

Stratification would be applied across the entire study, and not within an individual center, and will be reflected in the analytic model. The purpose of the a priori defined subgroup is for hypothesis generation.

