Withdrawal Criteria:	

• Unacceptable toxicity or AE.

• Clinically significant abnormal lab values:

○ Alanine aminotransferase (ALT) or aspartate aminotransferase (AST) <math>\geq</math> 8x upper limit of normal (ULN);

○ ALT or AST <math>\geq</math> 3x ULN and total bilirubin <math>\geq</math> 2x ULN at the same visit;

○ ALT or AST <math>\geq</math> 3x ULN with the appearance of symptoms indicating hepatitis (e.g., worsening fatigue, nausea, vomiting, right upper quadrant pain or tenderness, fever, rash, or eosinophilia).

	

• QT syndrome, Fridericia's formula corrected QT (QTcF) interval <math>\geq 470</math> ms (for male subjects) or <math>\geq 480</math> ms (for female subjects), or torsades de pointes.

• A positive urinary drug screen at any visit.

• Patient withdrawal of consent: at any time, a patient's participation in the study may be terminated at his/her request or on the basis of the Investigator's clinical judgment. The reason for patient withdrawal will be noted on the electronic case report form (eCRF).

• Intercurrent illness: a condition, injury, or disease unrelated to the primary diagnosis that became apparent during treatment and necessitated the patient's termination from the study.

• General or specific changes in the patient's condition that renders him/her ineligible for further treatment according to the inclusion/exclusion criteria.

• Patient fails to adhere to the protocol requirements (e.g., drug noncompliance, failure to return for defined number of visits).

• Lost to follow-up: the patient stopped coming for visits, and study personnel were unable to contact the patient.

• Pregnancy.

Planned Sample Size:	114 patients (38 per treatment group). This may be increased following a sample size re-estimation up to a maximum of 171 patients.
Investigational Therapy:	

• 2 mg SUVN-G3031

• 4 mg SUVN-G3031

Reference Therapy:	Placebo
Treatment Duration:	Each patient will be dosed for 14 days. The study is expected to last a total of 13 months.
Efficacy:	Efficacy assessments include MWT, CGI-S, ESS, CGI-C, PGI-C, nocturnal overnight PSG, and sleep diary.

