## 7.2.2 Assessments

### 7.2.2.1 Primary Outcome Measure

The primary objective pivots upon changes in EDS in patients with Na-1 and Na-2. The primary outcome measure, the change in total ESS scores from baseline, is used to derive the primary dependent variable. A successful study requires demonstration of a statistically significant difference between treatment groups based upon the ESS as a single primary endpoint, using a prespecified analytic model and an intent-to-treat (ITT) dataset.

The ESS consists of 8 questions chosen on a priori grounds to represent activities with a wide range of different somnificities.

The ESS is a self-administered questionnaire wherein respondents are asked to rate on a 4-point scale (0–3) their usual chances of dozing off or falling asleep while engaged in 8 different activities (see [Section 11.3](#)). It is important that participants answer every question, as there is no method for interpolating item scores and a missed question results in an invalid test. Most people engage in the activities in the test at least occasionally, although not necessarily every day. The recall period for the test asks subjects to rate experiences taking place “in recent times,” which is purposefully vague and is meant to represent a few weeks to a few months. Within the study, the ESS will be completed weekly, consistent with the recall period. The ESS score (the sum of 8 item scores, 0–3) can range from 0 to 24. The higher the ESS score, the higher the person’s average sleep propensity in daily life, or their “daytime sleepiness.” The questionnaire takes no more than 2 or 3 minutes to answer. The ESS can be interpreted per the bullets below:

- 0 to 5 Lower Normal Daytime Sleepiness
- 6 to 10 Higher Normal Daytime Sleepiness
- 11 to 12 Mild EDS
- 13 to 15 Moderate EDS
- 16 to 24 Severe EDS

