#### **14.3.1 Analysis of Primary Efficacy Endpoint**

The primary efficacy endpoint is the change from baseline in the mean total ESS score at Day 14. A successful study requires demonstration of statistically significant differences between the combined SUVN-G3031 doses (2 mg and 4 mg) group and the placebo group at endpoint for the ESS.

The null (H0) and alternative (H1) hypotheses of the study are as follows:

H0: SUVN-G3031 and placebo do not differ in their change from baseline in the mean total ESS score at Day 14.

H1: SUVN-G3031 and placebo differ in their change from baseline in the mean total ESS score at Day 14.

The primary endpoint will be analyzed using a mixed model repeated measures (MMRM) analysis that includes the mean total ESS score from baseline to 7 days through to 14 days. This method is the preferred approach to longitudinal analysis because it utilizes observed data efficiently.

The model will include randomized treatment, visit and treatment-by-visit interaction as explanatory variables, stratification factor for cataplexy patient history (presence or absence) and baseline total ESS score as covariates. The participant effect will be assumed to be random, and an unstructured covariance structure will be assumed for within participant variation. The main comparison will be a contrast between treatment groups at 14 days. Least square mean changes will be estimated for SUVN-G3031 and placebo.

This analysis will be repeated for the ITT and PP populations.

Various sensitivity analyses will be performed using an analysis of covariance (ANCOVA) and multiple imputation pattern mixture model to handle missing data. Estimands specification and sensitivity analyses details will be included in the SAP.

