#### **3.4. Brief Description**

This is a Phase 2, double-blind, placebo-controlled, parallel-group, multicenter study to evaluate the safety, tolerability, PK, and efficacy of 2 mg and 4 mg SUVN-G3031 compared with placebo in subjects with narcolepsy with and without cataplexy. Subjects will be randomized at a ratio of 1:1:1 to 2 mg SUVN-G3031, 4 mg SUVN-G3031, or placebo. Subjects will be stratified based on whether they have narcolepsy with or without cataplexy (Na-1 or Na-2, respectively).

Each subject will receive study drug once daily, in a tablet formulation, for 14 days. Enough subjects will be screened to enable 114 subjects to be enrolled (38 per treatment group). A single, unblinded, interim analysis will be undertaken when approximately 50% of subjects have completed 14 days of treatment; this analysis will enable sample size re-estimation to occur if appropriate. A maximum of 57 additional subjects (19 subjects per treatment arm) will be enrolled to generate a total maximum study population of 171 subjects.

Subjects will be enrolled at approximately 65 sites in the United States and Canada. It is anticipated it will take 12 months to complete enrollment and 13 months to complete the entire study.

Each subject will complete 3 periods: Screening, Dosing Period and Safety Follow-up.

**Screening:** Subjects who have provided written informed consent will be screened up to 28 days

[figure not shown]
This document is confidential.

before enrollment. Eligible subjects will complete a washout period of  $\geq 14$  days for all agents targeting cataplexy and  $\geq 7$  days for all stimulants targeting EDS.

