### **3.6. Determination of Sample Size**

Sample size for the MWT which was the primary efficacy in the study until the change in primary efficacy endpoint (refer to section 2.3): This study plans to randomize 114 subjects, using 1:1:1 treatment allocation (stratified by atleast 30% each by reported cataplexy subject history, Na-1 or Na-2 respectively), 38 to each treatment group. Using an SD of 5.0, N = 38 randomized subjects per group will provide 80% power, to detect a treatment difference over placebo of 3.5 points or greater on the MWT at a 2-sided Type I error level of 0.05, assuming a dropout rate of 10%.

Because of the unknown prognostic importance of a history of cataplexy with EDS on study outcome, a stratification factor will be included based upon that clinical presentation. Stratification would be applied across the entire study, and not within an individual center, and will be reflected in the analytic model. The purpose of the a priori defined subgroup is for hypothesis generation.

Based on the unblinded interim analysis results sample size was re-calculated to maximum of 171 subjects (57 to each treatment group) on mean MWT as primary efficacy endpoint.

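### Does Protocol 14.1 need rewriting because it still rests the sample size on the MWT and 114 patients?

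*Protocol*

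**What the plan says.** Protocol 14.1 plans 114 patients, 38 per group, allocated 1:1:1. With an SD of 5.0 and 10% dropout this "will provide 80% power, to detect a treatment difference over placebo of 3.5 points or greater on the MWT". Alpha is 0.05, two-sided. The section does not call the MWT primary, does not say that it once was, and does not mention 171.

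Elsewhere the protocol is clear about the present design. Section 7.2.2.1 defines success "based upon the ESS as a single primary endpoint". Section 14.3.1 sets the comparison "between the combined SUVN-G3031 doses (2 mg and 4 mg) group and the placebo group at endpoint for the ESS". Sections 6.2.2 and 14.3.2 list the MWT as a secondary endpoint. The synopsis gives 114 and adds: "This may be increased following a sample size re-estimation up to a maximum of 171 patients". Section 7.1 repeats the ceiling of 171, and 14.6 gives it as up to 57 additional patients.

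SAP 3.6 repeats the calculation but introduces it as "Sample size for the MWT which was the primary efficacy in the study until the change in primary efficacy endpoint". It then reports that, after the unblinded interim analysis, the "sample size was re-calculated to maximum of 171 subjects (57 to each treatment group) on mean MWT as primary efficacy endpoint". SAP 3.4 keeps the earlier description, with the interim analysis still to come: "Enough subjects will be screened to enable 114 subjects to be enrolled (38 per treatment group").

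Protocol section 14 states that the SAP takes precedence where the two documents differ.

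**The concern.** A sample-size section should justify the test that decides the trial. Read by itself, 14.1 appears to justify something else: a different endpoint (MWT, not ESS), apparently a different contrast (one dose against placebo, not the pooled doses) and a different number (114, with no mention of a re-calculation). Both sizing steps, 114 and 171, used the MWT according to SAP 3.6, and the legible sample-size sections give no ESS difference or SD.

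If the trial were in fact undersized for its current primary test, or if the stated 80% were taken as the power of the ESS comparison, a reader could misjudge how informative a null result is. The two states of the SAP (3.4 and 3.6) could also leave doubt about the number being enrolled.

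**Working it through.** **Inputs.** Two-sided alpha 0.05, power 80%, difference 3.5, SD 5.0, dropout 10%, 38 per group: all from Protocol 14.1. Pooled 2:1 contrast: Protocol 14.3.1. Maximum of 171: Protocol synopsis and SAP 3.6.

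**1. Reproduce the 38.** For one active group against placebo, the normal approximation gives n = 2 × (1.960 + 0.842)² × (5.0/3.5)² = 2 × 7.85 × 2.04 = 32.0, so 33 evaluable, and 33/0.9 = 36.7, so 37 randomized. The noncentral t needs 34 evaluable, and 34/0.9 = 37.8, so 38 randomized, which is the plan's figure. Power with 34 against 34 is 81.2%.

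**2. Which contrast lies behind it?** Section 14.1 does not name one. On the same inputs:

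| Reading | Randomized per group |
|---|---|
| One dose vs placebo, two-sided 0.05 | 38 (noncentral t) |
| One dose vs placebo, one-sided 0.05 | 29 |
| Each dose at two-sided 0.025 | 44 |
| Pooled doses vs placebo, 2:1 | 28 |

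For the pooled row, 1.5 × 7.85 × 2.04 = 24.0, so 25 placebo patients, and 25/0.9 = 27.8. Only the first reading gives 38. One dose against placebo is therefore a good inference, but it is not written in the text.

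**3. Does the stale text flatter the trial?** Allow 10% dropout: 38 × 0.9 gives about 34 per arm, and 57 × 0.9 gives about 51. The standardized difference detectable with 80% power (noncentral t, two-sided 0.05) is:

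| Comparison | Evaluable | Detectable difference |
|---|---|---|
| One dose vs placebo, N = 114 | 34 vs 34 | 0.69 SD |
| Pooled vs placebo, N = 114 | 68 vs 34 | 0.59 SD |
| Pooled vs placebo, N = 171 | 102 vs 51 | 0.48 SD |

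The Cui-Hung-Wang (CHW) weighting costs little. Assume W1 = 0.5, with 17 evaluable per arm in stage 1 and 34 in stage 2 (57, then 114 randomized, less 10%). The pooled information is I = 1/(1/(2n) + 1/n), which is 11.33 and 22.67. The detectable difference is (1.960 + 0.842)/(√(0.5 × 11.33) + √(0.5 × 22.67)) = 2.802/5.747 = 0.49 SD, against 0.48 for the unweighted normal test.

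The documents give no ESS SD in legible text. If it were 4 to 6 points (an assumption), these values would be about 2.4 to 3.6 ESS points at N = 114 and 1.9 to 2.9 at N = 171.

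**4. Reconcile 114 and 171.** 114 + 57 = 171 and 3 × 57 = 171, so the synopsis, Protocol 14.6 and SAP 3.6 agree on the ceiling. The texts differ only in whether they speak from before or after the interim analysis.

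**The case for a change.** The best case for a change is this. Precedence of the SAP settles which text governs, but it does not tell someone reading the protocol that 14.1 is historical, and it cannot settle SAP 3.4 against SAP 3.6, since both are in the SAP. SAP 3.6 says the re-calculation treated the MWT as primary, so the change to the ESS appears to have come after an unblinded look. A reader will then want to know exactly what the trial was sized for. The protocol supplied here already has the ESS as primary, so it could have carried the label. No blacked-out text in 14.1 explains its absence.

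Part of this stands. The label is missing from 14.1, and SAP 3.4 and 3.6 describe different stages. The order of events is an inference, because SAP 2.3, to which 3.6 refers, is blacked out.

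The rest carries less weight. Section 14.1 names the MWT openly, so it does not pass the figure off as ESS power, and the same protocol states the primary endpoint, the pooled contrast and the ceiling of 171. Section 7.1 sends the reader to both 14.1 and 14.6. Only someone reading 14.1 in isolation would be misled. Setting one current number everywhere is also less simple than it sounds: being re-calculated to a maximum of 171 may mean that 171 was adopted, or only that the ceiling was confirmed.

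An ESS power sentence added now would be retrospective, would rest on an assumed SD and would inform no decision. SAP 2.3, 11.1 and 12 are not legible and may already hold an ESS rationale, so none can be called missing.

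**Conclusion.** No change to the plan is needed. The stated power is correct for the comparison that reproduces it (81% against a claimed 80%). The SAP, which prevails, labels that comparison as belonging to the former primary endpoint. The slip is clerical: one missing label in Protocol 14.1 and one un-updated descriptive paragraph in SAP 3.4. Its effect on the type I error rate, the model, the testing order and the result is nil. In SD units the current primary comparison is more sensitive than the one behind the 38 (0.48 to 0.59 SD against 0.69 SD).

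This rests on four assumptions: 10% dropout in every arm; a plain two-sample comparison in place of the baseline-adjusted MMRM; for the CHW figure, an interim analysis at half the original information; and one dose against placebo as the original contrast, which is inferred. The comparison in SD units does not depend on the assumed ESS SD. If either document is reopened for another reason, copying the SAP 3.6 label into 14.1 and stating whether 171 was adopted would be tidy, but nothing in the conduct or interpretation of the trial waits on it.
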